## 7.6 Discontinuations

If a subject is withdrawn before completing the study, the reason for withdrawal will be entered on the appropriate eCRF. The specific reason for the withdrawal should be documented on the eCRF. For instance, rather than stating “withdrew informed consent,” the specific reason for withdrawing the informed consent should be stated. Whenever possible and reasonable, the evaluations that were to be conducted during the final study visit should be performed at the time of premature discontinuation.

It is vital to obtain follow-up data on any subject who terminated because of an AE, abnormal laboratory test, or ECG finding. In any case, every effort must be made to ensure safety follow-up procedures are completed.

## **8 QUALITY CONTROL AND ASSURANCE**

The study will be conducted according to GCP guidelines and according to national law. Quality control audits may be performed at the discretion of Jazz Pharmaceuticals.

## 9 PLANNED STATISTICAL METHODS

### 9.1 General Considerations

All study data will be summarized by treatment or treatment sequence as appropriate. Categorical variables will be reported as frequency and percent (e.g., gender, race). Continuous variables will be reported as number of subjects with observations, mean, standard deviation (SD), median, minimum and maximum (e.g., age, weight). Listings will include the group number (e.g., Group 1 or Group 2) in which a subject was enrolled. All summaries, statistical analyses, and individual subject data listings described in this section will be produced using Version 9.3 or later of the SAS Statistical Analysis System (SAS Institute, Inc. Cary, NC).

### 9.2 Tests of Hypotheses and Significance Levels

Safety and tolerability of JZP-110 is the primary objective of this study. No inferential statistics will be provided for safety endpoints.

To address the key efficacy objective of treatment effect on the change in ESS in an exploratory manner, pairwise treatment difference against placebo will be tested as part of the mixed-effects model described in [Section 9.12](#) using a 2-sided test at 0.05 level.

### 9.3 Determination of Sample Size

Approximately 49 subjects will be randomized to the 3 sequence groups (A, B, and C) with the goal of 40 subjects completing the study: 34 subjects each in Sequences A and B, and up to 6 subjects in sequence C. The randomization ratio implemented will be 3:3:1 with expected randomization of subjects to sequences being approximately 21:21:7.

Although the primary objective of this study is to assess safety, efficacy endpoint-based power calculations were performed for reference. A sample size of 34 subjects (assuming 17 completing in each of the Sequences A and B) will provide 80% power to detect a difference of 3 points in the change from baseline in ESS score between 1 of the JZP-110 and placebo groups not adjusting for multiple comparisons. This calculation assumes a common SD of 6 points for the change from baseline in ESS score and a 2-sided significance level of 0.05 using an analysis of variance (ANOVA)-based t-test for difference of means in a crossover design. The primary purpose of placebo Sequence C is to preserve study blinding.

### 9.4 Analysis Populations

The safety population will consist of all subjects who received at least 1 dose of study drug. This population will be analyzed for safety evaluations and will be presented in the tables and listings of safety data.

The modified intent-to-treat (mITT) Population will include subjects who were randomized, received at least 1 dose of study medication and have baseline and at least 1 postbaseline evaluation of ESS. This population will also be analyzed for exploratory efficacy endpoints.

The PK population will consist of all subjects who enrolled under the Original Protocol or Amendment 1 and received study drug and provided postdose PK data for at least 1 time point.

The key efficacy population will consist of subjects in the mITT population from Sequences A and B only. Exploratory efficacy analyses will be performed on subjects from sequences A, B, and C. The details of how these populations are defined will be specified in the Statistical Analysis Plan.

## **9.5 Demographics and Baseline Characteristics**

Demographics and baseline characteristics will be summarized for the safety population and the mITT population. The summaries of data will include frequencies and percentages for categorical variables and mean, SD, median, minimum and maximum for continuous variables.

## **9.6 Handling of Dropouts and Missing Data**

All available data will be presented in descriptive summaries and included in statistical models as appropriate. All subjects who are included in the safety, mITT, or PK population will be included in analyses, and their missing data will not be imputed.

## **9.7 Pooling of Investigation Centers**

Data from all investigational centers will be pooled together for all analyses.

## **9.8 Primary Objective**

The primary objective of this study is the safety and tolerability of JZP-110 administered to subjects with excessive sleepiness and PD. This will be assessed by the occurrence of and/or clinically significant changes in:

- Treatment-emergent AEs
- Discontinuations due to AEs
- Clinical laboratory tests (chemistry, hematology, and urinalysis)
- Vital signs
- 12-lead ECGs
- Physical examination
- C-SSRS

## **9.9 Key Efficacy Endpoint**

The key efficacy endpoint is defined in terms of change from study baseline (prior to first dose in Period 1) to the end of each Treatment Period (Weeks 1, 2, 3, and 4); and consists of the following:

- Change from Baseline in ESS (Epworth Sleepiness Scale) score

## 9.10 Exploratory Endpoints

Exploratory efficacy endpoints include the following as measured by the change from Baseline in scores (prior to first dose in Period 1) to the end of each Treatment Period (Weeks 1, 2, 3, and 4) for each of the following assessments:

- Mean sleep latency time (in minutes), as determined from the 40-minute MWT
- MDS-UPDRS Parts III and IV
- CGIc
- PGIC
- FSS
- Apathy Scale
- SCOPA-cog

## 9.11 Pharmacokinetic Analysis

Pharmacokinetic analysis will include estimation of the following parameters of interest:  $C_{max}$ ,  $T_{max}$ ,  $t_{1/2}$ , and area under the curve (AUC), as appropriate. Pharmacokinetic parameters will be estimated for subjects in the PK population who have evaluable PK data.

## 9.12 Efficacy Analysis

For the analysis of the key efficacy endpoints of change from baseline in ESS, a mixed-effects model will be used as the primary method of analysis. This model will include fixed effects for treatment (dose), sequence, treatment-by-sequence interaction, and baseline value of the efficacy endpoint. The model will also include a random effect for subject within sequence.

SAS procedure PROC MIXED will be used to carry out this analysis. All available data will be included in the model. The estimates of treatment difference versus placebo and associated 95% confidence intervals will be presented.

Additional statistical methodologies will be explored to aid in the interpretation of the study results due to treatment-by-sequence interaction and carryover effects. The details will be provided in the Statistical Analysis Plan.

For the analysis of the MWT exploratory endpoint, a similar mixed-effects model as for ESS will be used. However, because the MWT will be optional and consequently result in a reduced sample size, there may be convergence issues associated with the mixed-effects model. In the event such issues do arise, an analysis of covariance (ANCOVA) model without accounting for treatment sequence may be used at each visit.

For the analysis of efficacy endpoints of improvement in PGIC and CGIc, the chi-squared test will be used to test the hypotheses of difference between placebo and each active dose.

A mixed-effects model similar to the model described above will be used for the analysis of MDS-UPDRS, FSS, Apathy Scale, and SCOPA-cog endpoints. Details of the analyses will be specified in the Statistical Analysis Plan.

As a sensitivity analysis, the efficacy endpoint summary may be reported separately for Groups 1 and 2 to address any potential selection bias.

In addition, due to the removal of MWT as an eligibility criterion in Protocol Amendment 2, the efficacy endpoint summary may also be reported separately for subjects with eligible MWT at study entry versus those with either ineligible or missing MWT at study entry.

No adjustment for multiple testing will be performed.

Summary statistics for all efficacy assessments/endpoints will be presented by treatment dose.

## **9.13 Safety Analysis**

### **9.13.1 Adverse Events**

Adverse events will be coded using the Medical Dictionary for Regulatory Activities system to classify events under primary system organ class and preferred term. The number and percent of subjects who experienced TEAEs, TEAEs related to study drug, or SAEs; who died during the study; or who discontinued study drug or withdrew from the study due to an AE will be summarized by treatment at onset. Results will be presented by system organ class, and preferred term.

A TEAE is defined as an AE that either began after first study drug dose or worsened after the first dose. When determining the percent of subjects who experience an AE, multiple increases in severity are only counted as one AE. For example, a subject who develops a mild headache after the first study drug dose (that was not present during screening or at baseline), which subsequently worsens to moderate, then severe, is only counted once under the preferred term of headache.

For all AE summaries, if a subject has more than one AE within a preferred term on a given dose, the subject is counted only once at the maximum severity and with the closest relationship to study drug. If a subject has more than one AE within a system organ class, the subject is similarly counted once when reporting results for that system organ class.

All AE data will be listed.

### **9.13.2 Vital Signs**

Vital signs will be summarized at baseline, at each postbaseline visit, and within each visit across time. Change from baseline to each postbaseline visit in each vital sign parameter will also be summarized. The summaries will include descriptive statistics (i.e., mean, median, minimum, maximum, SD, and number of subjects) as well as graphs, and will be presented by treatment (dose) group, and by sequence.

The number and percentage of subjects with clinically significant changes from baseline to each postbaseline visit in blood pressure and heart rate will be summarized. The ranges will be prespecified in the Statistical Analysis Plan.

Blood pressure and heart rate will also be categorized as falling within or outside of normal ranges. Frequency counts and percentages will be presented by treatment (dose) group, and by sequence. In addition, shifts in these categories from baseline to each postbaseline visit will be summarized by treatment (dose) group and by sequence group. The ranges will be prespecified in the Statistical Analysis Plan.

The blood pressure and pulse results obtained on MWT days will be summarized separately, in a similar fashion.

In addition, blood pressure and heart rate will be analyzed separately for the subset of subjects who meet criteria for clinically significant orthostatic hypotension.

A listing of subjects who have clinically significant vital sign values will be generated.

Detailed vital signs analyses, and the statistical derivation of the algorithms to be used to derive variables for clinically significant changes will be specified in the Statistical Analysis Plan based on data observed in other JZP-110 studies during the conduct of this study.

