At Visits 3, 4, 5, and 6, body temperature, respiratory rate, blood pressure (seated and standing), and pulse (seated and standing) will be taken approximately 1 hour prior to dosing at the clinic. For subjects enrolled in Group 1, blood pressure (seated and standing) and pulse (seated and standing) will also be taken approximately 1, 2, 4, and 6 hours after dosing as described in [Appendix 3](#). For subjects enrolled in Group 2, blood pressure (seated and standing) and pulse (seated and standing) will also be taken approximately 1 and 2 hours after dosing as described in [Appendix 6](#).

Body temperature, respiratory rate, and blood pressure (seated and standing) and pulse will also be obtained on admission to the site in the morning at the Follow-up visit.

The schedule of assessment for vital signs for subjects enrolled in Group 1 is described in [Section 7](#), Appendix 2, and Appendix 3. The schedule of assessment for vital signs for subjects enrolled in Group 2 is described in Section 7, Appendix 5, and Appendix 6.

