## 6.9 Electrocardiography

Standard 12-lead ECGs will be recorded with the subject resting supine for at least 5 minutes. ECGs will be performed at every clinic visit. The schedule of ECG assessment is described in [Section 7](#), [Appendix 2](#) (Group 1), [Appendix 3](#) (Group 1), [Appendix 5](#) (Group 2), and [Appendix 6](#) (Group 2). In addition to local assessment by the principal investigator, a core laboratory will independently assess all Baseline and post-Baseline ECGs for calculation of changes from Baseline.

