## 7.4 Follow-up (Day 35 [ $\pm 1$ day]) (For Subjects in Both Groups 1 and 2)

At the Follow-up Visit, perform the following:

- Record all concomitant medications, including OTC medications, health, and dietary supplements taken since the last visit.
- Complete physical examination.
  - Obtain weight in ordinary indoor clothes (without shoes).
- Obtain vital signs (systolic and diastolic blood pressure [seated and standing], pulse rate [seated and standing], respiratory rate, and body temperature), including at least 2 sets of blood pressure and pulse rate measurements in the seated position after the subject has been resting and seated for at least 5 minutes. Next, standing blood pressure and pulse rate should be taken at 1 and 3 minutes after the subject has been standing.
- Obtain a 12-lead ECG after the subject has been resting supine for at least 5 minutes.
- Obtain safety laboratory blood samples for serum chemistry and hematology tests and a urine sample for urinalysis.
- Obtain a urine sample for a pregnancy test for all females of childbearing potential (see [Table 1](#) for definitions of childbearing potential).
- Complete breath alcohol screen test.
- Administer the C-SSRS Since Last Visit Version and record the results.
- Complete the ESS Questionnaire.
- Document any AEs that occurred since the last visit. Document the outcome of any ongoing AEs.

Unless any safety issues are identified that require follow-up, the study will be considered completed and the subject will be discharged from the study. Subjects will be instructed to follow-up with their healthcare provider regarding the resumption of any medications that were discontinued prior to study participation.

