### 9.13.4 12-Lead Electrocardiograms

Electrocardiogram intervals and durations will be reviewed for notable abnormalities, and clinically notable abnormalities and findings considered to be clinically significant will be listed. The number and percent of subjects who have a clinically notable ECG interval abnormality or other clinically significant ECG finding will be summarized. A listing of abnormal ECG values will also be provided. Detailed ECG value analyses and the algorithms to derive variables for the clinically significant changes will be specified in the Statistical Analysis Plan.

Electrocardiogram parameter values (HR, RR, PR, QRS, QT, and QT corrected with Fridericia's formula [QTcF]) will be summarized at baseline, at each postbaseline visit, and within each visit across time by treatment group (dose) and by sequence. The number and percentage of subjects with QT and QTcF values falling within or outside of normal ranges will be summarized by treatment (dose) groups and by sequence. The number and percentage

of subjects with other clinically significant ECG findings will also be summarized at each postbaseline time point by treatment (dose) and by sequence group.

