### 17.3. ECG EVALUATIONS

The following ECG parameters will be reported for this study based on core laboratory values:

- HR (beats per minute [bpm])
- RR interval (msec)
- PR interval (msec)
- QRS interval (msec)
- QT interval (msec)
- QT Fridericia's correction (QTcF) interval (msec) [derived]
- QT Bazett's correction (QTcB) interval (msec) [derived]
- Overall evaluation of ECG:
  - Normal
  - Abnormal, not clinically significant
  - Abnormal, clinically significant

The following summaries will be provided based on SAF for ECG data:

- Observed values and change from Baseline to end of period post-dose timepoint (for quantitative measurements)
- Observed values and change from end of period pre-dose timepoint to end of period post-dose timepoint (for quantitative measurements)
- Incidence of markedly abnormal criteria from Baseline to end of period post-dose timepoint (refer to Section 17.3.2 for details) by gender
- Incidence of markedly abnormal criteria from end of period pre-dose timepoint to end of period post-dose timepoint (refer to Section 17.3.2 for details) by gender
- Shift from Baseline to end of period post-dose timepoint in ECG overall evaluation by gender
- Shift from end of period pre-dose timepoint to end of period post-dose timepoint in ECG overall evaluation by gender

- Incidence of subjects for which their ECG overall evaluation improved, remained unchanged or worsened from Baseline to end of period post-dose timepoint by gender
- Incidence of subjects for which their ECG overall evaluation improved, remained unchanged or worsened from the end of period pre-dose timepoint to the end of period post-dose timepoint by gender
- Incidence of subjects with at least one ECG diagnosis by diagnosis category (i.e., rate/rhythm, conduction abnormalities, changes in ST segment, axis, chamber enlargement, myocardial infarction, and miscellaneous) and diagnosis by visit, timepoint, and gender

The following listings will be provided:

- Listing of subjects with any observed QT, QTcB, or QTcF values >450 msec and/or change from Baseline in QT, QTcB, or QTcF >30 msec
- Listing of subjects with any abnormal ECG overall evaluation

The following figures will be provided:

- Line plot of mean observed values across visit by sequence and treatment group;

[figure not shown]

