### 17.4.2. SEATED BLOOD PRESSURE AND PULSE RATE

The average of all measurements collected during the Baseline visit and of all measurements collected during the end of period visit post-dose timepoints will be computed and the following summaries will be provided:

- Average observed values and average change from Baseline to the end of period visit;
- Shift from Baseline to end of period visit when average observed values are categorized into Low/Normal/High (refer to Table 6);
- Incidence of subjects with average change from Baseline to end of period visit meeting the following criteria:
  - Decrease/increase in SBP  $\geq 10$ ,  $\geq 20$ , and  $\geq 30$  mmHg
  - Decrease/increase in DBP  $\geq 10$ ,  $\geq 20$ , and  $\geq 30$  mmHg
  - Decrease/increase in pulse rate (HR)  $\geq 15$  and  $\geq 30$  beats per minute

The average of the 2 (or 3, when applicable) measurements collected during each end of period visit pre-dose and post-dose timepoints will also be computed and the following summaries will be provided:

- Average observed values and average changes from the end of period visit pre-dose timepoint to each end of the period visit post-dose timepoint;

- Average observed values and average changes from each baseline visit timepoint to time-matched end of period visit timepoint, where the 0-hour baseline timepoint is matched with the pre-dose end of period visit timepoint, the 2-hour baseline timepoint with the 1-hour post-dose end of period timepoint, the 3-hour baseline timepoint with the 2-hour post-dose end of period visit timepoint, and the 5-hour baseline timepoint with the 4-hour post-dose end of period timepoint;
- Shift from end of period visit pre-dose timepoint to each end of period post-dose timepoint when average observed values are categorized into Low/Normal/High (refer to Table 6);
- Shift from each baseline visit timepoint to time-matched end of period visit timepoint when average observed values are categorized into Low/Normal/High;
- Incidence of subjects with average change from end of period pre-dose timepoint to each end of period visit post-dose timepoint meeting the criteria described above;
- Incidence of subjects with average change from each Baseline timepoint to time-matched end of period visit timepoints meeting the criteria described above

The following listings will be provided:

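### The SAP's seated blood pressure, pulse and ECG-interval tables stop at the end-of-period visits, so the off-drug Day 35 readings enter no change-from-baseline table, although the protocol covers each postbaseline visit

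*Protocol*

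**What the plan says.** **Protocol, analysis.** For vital signs, 9.13.2 states: "Change from baseline to each postbaseline visit in each vital sign parameter will also be summarized". The same section promises clinically significant changes and category shifts in blood pressure and heart rate to each postbaseline visit. For ECG, 9.13.4 says that parameter values "will be summarized at baseline, at each postbaseline visit, and within each visit across time by treatment group (dose) and by sequence". That sentence promises values, not changes. Section 6.9 adds that "a core laboratory will independently assess all Baseline and post-Baseline ECGs for calculation of changes from Baseline".

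**Protocol, collection.** Section 6.9 states that "ECGs will be performed at every clinic visit". Section 6.5 says that temperature, respiratory rate, seated and standing blood pressure, and pulse "will also be obtained on admission to the site in the morning at the Follow-up visit". Section 7.4, which opens "At the Follow-up Visit, perform the following", lists both the vital signs and a 12-lead ECG. Appendices 1 and 4 show both at Visit 7 for Groups 1 and 2.

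**SAP.** For seated blood pressure and pulse, the leading table in 17.4.2 is "Average observed values and average change from Baseline to the end of period visit". It is built from the post-dose timepoints of that visit. For ECG intervals, 17.3 begins with "Observed values and change from Baseline to end of period post-dose timepoint (for quantitative measurements". The other change, shift and threshold summaries in these two sections also end at an end-of-period pre-dose or post-dose timepoint.

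**The concern.** Safety and tolerability are the primary objective. Protocol 1.3.6 describes blood pressure and heart rate effects in earlier studies as small and short-lived. Visit 7 is where this trial could check, in subjects whose last week was on 300 mg, whether any such change has gone once the drug has cleared. The data are collected, but the SAP sends them to no change table, and it does not say that it has narrowed what the protocol promised.

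At stake is a tabulated off-drug change after 300 mg for Sequence A, half of the subjects planned to receive active drug. The on-treatment safety tables are unaffected.

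**Working it through.** The plan gives no figure to reproduce here. The check is mainly a comparison of texts, with short calculations on timing and size.

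**1. Is Day 35 a postbaseline visit?** Yes, on the plain reading. It is a numbered clinic visit after Baseline, and SAP Table 4 gives it a window with target day 35. Where the protocol means only Weeks 1 to 4 it says so: the efficacy endpoint in 9.9 is tied to the end of each treatment period.

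**2. Is it off drug?** The inputs are about 7 days since the last dose (Protocol 3.1) and a half-life of 5 to 7.6 hours (Protocol 1.3.1).

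- Elapsed time: 7 × 24 = 168 hours.
- Half-lives elapsed: 168 / 7.6 = 22.1 to 168 / 5 = 33.6.

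**3. Can the SAP's table definitions take in Day 35?** Taken alone, the words end of period might be stretched to the end of the follow-up period. The definitions in 17.3 and 17.4.2 rule this out because they require pre-dose or post-dose timepoints, and no dose is given at Visit 7. Elsewhere the SAP reaches follow-up clearly:

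| SAP section | Data | Reaches follow-up? |
|---|---|---|
| 16.1.4 | ESS change | Yes, follow-up is named |
| 17.1 | Treatment-emergent adverse events | Yes, with a separate overall summary |
| 17.2 | Laboratory change | Yes, tabulated by visit |
| 17.4.2 | Seated blood pressure and pulse change | No |
| 17.3 | ECG-interval values and change | No |

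**4. Is the omission declared?** No. SAP 3.6 lists other changes of similar size, including dropping by-sequence vital-sign and ECG summaries (placebo excepted) and dropping the count of abnormal laboratory values. It does not mention Visit 7.

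**5. Who loses a reading?** Planned allocation is 21:21:7. Sequence B takes its last 300 mg dose on Day 21 and is measured on placebo on Day 28, also about 168 hours later. SAP 17 splits placebo by sequence, so that reading sits in a planned change column. Sequence A ends on 300 mg at Day 28, and Day 35 is its only off-drug reading after that dose. The share affected is 21 / (21 + 21) = 50% of Sequences A and B.

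**6. Does the Day 28 pre-dose reading stand in for Day 35 in Sequence A?** Not well. It falls about 24 hours after the Day 27 dose: 24 / 7.6 = 3.2 to 24 / 5 = 4.8 half-lives. The fraction of that dose remaining is 0.5^3.2 to 0.5^4.8, about 11% to 4%. It is a trough during daily dosing, not a reading after stopping.

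**7. How precise would the added table be?** The planned number of completers in Sequence A is 17 (SAP 3.4). The documents give no SD for change in systolic pressure, so assume 8 to 14 mmHg. The standard error of the mean change is SD / √17: 8 / 4.12 = 1.9 mmHg to 14 / 4.12 = 3.4 mmHg.

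**The case against.** **The trial does show reversal.** A reader might infer that, without a Day 35 table, the trial cannot say whether effects on blood pressure, pulse or QTcF go away. The documents do not support that. Sequence B's Period 4 placebo column gives blinded change from Baseline about a week after 300 mg, with several timepoints, in a planned 21 subjects. This stands, and it limits the point to Sequence A. The column does lack a concurrent unexposed comparison: at Week 4 Sequence A is on 300 mg, and Sequence C's descriptive values are averaged over all four periods (SAP 17).

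**The ECG promise is weaker.** A reader might also infer that the protocol promises ECG change at each postbaseline visit. Section 9.13.4 promises values only, and 6.9 speaks of core-laboratory reading so that changes can be calculated. This also stands. A gap remains, because the interval tables in SAP 17.3 restrict observed values, as well as changes, to end-of-period timepoints.

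**Day 35 is partly visible elsewhere.**

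- SAP 17.3 lists subjects with any QT or QTc value above 450 msec, or an increase above 30 msec, without limiting the visit. It also plots mean ECG values across visits by sequence and tabulates ECG diagnoses by visit.
- SAP 17.4.3 summarises observed values and seated-to-standing change by timepoint and visit.
- Clinically significant adverse changes in ECG or vital signs are adverse events (Protocol 6.14.1), and SAP 17.1 summarises events starting in follow-up.

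All of this is true. None of it is a change-from-baseline table for seated pressure, pulse or ECG intervals.

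**The table shells are not available here.** SAP 8 says that the shells set the content of the outputs. The finding is therefore about the SAP text; a shell that already includes Visit 7 would meet the need for the table.

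**Conclusion.** The point holds in a limited form. The protocol commits to vital-sign change from baseline, and to ECG values, at each postbaseline visit. The SAP text stops both at the end-of-period visits and does not declare it. Day 35 enters no change-from-baseline table for seated blood pressure, pulse or ECG intervals. For the 21 subjects planned in Sequence A, no table shows off-drug change after 300 mg; Sequence B's Period 4 placebo column is the only one that does so in this trial.

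This rests on reading postbaseline visit to include Visit 7 and on the SAP text without its shells. The half-life is the one the protocol reports from earlier studies.

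A reader might go further and want a formal comparison at Day 35 of Sequence A with Sequences B and C as controls. The documents do not support that either. Protocol 9.2 excludes inferential statistics for safety. Sequence B at Day 35 is only about 14 days past its own last 300 mg dose (Day 35 minus Day 21), so it is not an unexposed group.

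The gap is worth closing because it concerns the primary objective and the data are already collected.

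**What to change.** In SAP 17.4.2 and 17.3, add for Visit 7 the observed value and change from Baseline, descriptively, for seated systolic and diastolic pressure, pulse, heart rate and QTcF. Apply the threshold incidences already defined in 17.4.2 and 17.3.2.

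- **Reference.** For blood pressure and pulse use the Baseline arrival set (the 0-hour Baseline timepoint in 17.4.2), because Visit 7 has a single set taken on morning arrival. Do not use the Day 28 pre-dose reading as the reference: it compares a nearly cleared state with a cleared one.
- **Layout.** Present by last treatment received, with placebo split by sequence: Sequence A after 300 mg, and Sequences B and C after placebo. This follows the SAP's rule for follow-up adverse events (17.1) and its placebo split (3.6 and 17). Footnote that Sequence B is about 14 days past its last 300 mg dose.
- **Scope.** Add no confidence interval or test between sequences. Observed orthostatic values by visit are already planned in 17.4.3.

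The cost is SAP wording and a few extra descriptive tables, with modest precision. No new procedure is needed. Declaring the omission in SAP 3.6 would settle the inconsistency, but would leave Sequence A's off-drug change untabulated.
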